#### HB-adMSCs - Placebo

Pairwise t-test will be performed on the efficacy endpoints to test the difference between baseline and week 52 (EOS) as secondary analysis. Data for all the efficacy outcomes will be checked for normality (Shapiro-Wilk Test). When there is a larger deviation of data distribution from normality, appropriate non-parametric test will be used.

Additionally, RMA and ANCOVA in a Bayesian framework using a non-informative prior will be conducted to estimate the posterior distribution and to estimate the probability that the true treatment difference of change from baseline to Week 4, Week 8, Week 16, Week 24, Week 32, Week 42 and Week 52.

Study population analyses including analyses of subject disposition, demographic and baseline characteristics, medical history, prior and concomitant medications.

Disposition summary includes, subject screened, randomized and disposition at end of study – Week 52 along with reasons for withdrawals. Subjects in different analysis populations also will be presented.

The screen failure table includes total number of screened subjects and reasons. The percentage in the screen failure table will be calculated based on total number of screened subjects as denominator.

#### 5.1.2. Baseline Definitions

For all endpoints, the baseline value will be the latest pre-treatment assessment visit with a non-missing value. i.e., If an assessment has been made both at screening visit (Visit 1) and Week 0 infusion 1 visit (Visit 2, Week 0), the value from the Week 0 visit is used as the baseline value. If the value measured at the Week 0 visit is missing and

the assessment also has been made at screening, then the screening value is used as the baseline value.

Unless otherwise stated, if baseline data is missing no derivation will be performed and baseline will be set to missing.

Change from baseline calculated as: Post-baseline value – Baseline

## 5.2. Primary Endpoint(s) Analyses

The primary objective of this study is to compare HB- adMSCs to Placebo on Multiple Sclerosis Quality of Life (MSQOL)-54 Instrument scores. Efficacy analysis set will be used for this analysis. The details of the planned displays are in programming specification document.

### 5.2.1. Definition of endpoint(s)

Objectives	Endpoints
Primary Objective	Primary Endpoint

To investigate the efficacy of intravenous infusions of HB-adMSCs vs Placebo in patients with Multiple Sclerosis as determined by improvements in Multiple Sclerosis Quality of Life (MSQOL)-54 Instrument. (Time frame: Baseline to Week 52).

	

Changes from Baseline at Weeks 52 in Multiple Sclerosis Quality of Life (MSQOL)-54 Instrument scores following treatment with HB-adMSCs or Placebo.

 
This 54-item questionnaire provides 12 subscales, two summary scores, and two extra single-item measures. The subscales are physical function, role limits-physical, emotional role restrictions, pain, emotional well-being, energy, health perceptions, social function, cognitive function, health distress, overall quality of life, and sexual function.

Data from the MSQOL-54 will be scored according to the scoring algorithm suggested by the authors of the questionnaires ([Vickrey](#) 1995). Scale scores will be generated by averaging the items within scales and transforming the mean scores linearly from 0 to 100 possible scores, with higher scores indicating a better QOL. Physical and mental health composite scores will be generated by weighting the sum of selected scales to generate a simplified two-factor solution and the composite scores of the MSQOL-54.

### Derivation of MSQOL-54 Composite Scores

Two composite scores are defined for MSQOL-54 using the subscale scores defined in the table below. The MSQOL-54 Physical Health Composite score and the MSQOL-54 Mental Health Composite Scores are calculated as a weighted-sum using the subscale scores and the weights defined in table below. If a subscale score is missing then it will not contribute to the Composite Score calculation (in effect, it is treated as a score of 0).

Composite Score	Subscale	Weight for Composite
Physical Health	Physical Function	0.17
	Health Perceptions	0.17
	Energy	0.12
	Role Limitations - Physical	0.12
	Pain	0.11
	Sexual Function	0.08
	Social Function	0.12
	Health Distress	0.11
Mental Health	Health Distress	0.14
	Overall Quality of Life	0.18
	Emotional Well-being	0.29
	Role Limitations - Emotional	0.24
	Cognitive Function	0.15

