9-Hole Peg Test		X		X		X		X	X
Multiple Sclerosis Quality of Life Inventory 54		X		X		X		X	X
Patient Health Questionnaire 9 (PHQ-9)		X							X
Study Treatments Administration		X	X	X	X	X	X		
24 hours Telephone Encounter		X	X	X	X	X	X		
Video Documentation		X				X			X
AE and SAE assessments		X	X	X	X	X	X	X	X

¹ Collection of laboratory samples (CBC, CMP & Coagulation Panel)

Study Visits 1 to 9.

Visit 1 – Screening.

At the Screening Visit (Visit 1), study participants' information will be collected by study's delegated personnel for evaluation of trial eligibility. The following information is required to determine eligibility:

1. Signing Informed Consent Form (prior to any trial-related activities).
2. Collection of demographic information, such as age, race, ethnicity, date of birth, gender, and relevant medical and surgical history.
3. Collection of Medical History and concomitant medications, including relevant information about the past and present health of study participants.
4. Inclusion and Exclusion criteria evaluation.
5. Measurement of vital signs including respiratory rate, body temperature, blood pressure, pulse rate, oxygen saturation, and measurement of weight and height.
6. Collection of laboratory samples, including Comprehensive Metabolic Panel (CMP), Complete Blood Count (CBC), Coagulation Panel, and Urine pregnancy test if female of childbearing potential.
7. Physical examination by Principal Investigator, including clinical assessments such as Expanded Disability Status Scale (EDSS).

Within 28 days of the Visit 1 - Screening, the principal investigator must decide participant's eligibility. Once, the eligibility of the subject has been confirmed by the principal investigator, the randomization process will be conducted.

Visit 2 and 6 – Infusion 1 (Baseline) and Infusion 5

The following procedures are required during this visit:

1. Update medical history and concomitant medications if any change occurred since last visit.
2. Measure vital signs including respiratory rate, body temperature, blood pressure, pulse rate, oxygen saturation and measurement of weight.
3. Collect laboratory samples, including Comprehensive Metabolic Panel (CMP), Complete Blood Count (CBC), Coagulation Panel and Urine pregnancy test if female of childbearing potential.

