#### 5.1.1. General Methodology

Unless otherwise stated, all hypotheses will be tested at a 2-sided significance level of 0.05 and 95% confidence interval. All continuous measurements will be summarised descriptively at each visit by treatment using observed data.

Summary of continuous variables will be presented using N, Mean, 95% confidence interval of mean, Standard Error of mean (SE), Standard Deviation (SD), Median and Range (Minimum and Maximum). The categorical variables will be presented using number and percentage based on N.

For measurements over time mean values will be plotted to explore the trajectory over time. Observed data will be used as the basis for plotting data along with bars as +/- SE, not otherwise specified.

As a primary analysis, a standard Analysis of Covariance (ANCOVA) will be applied for primary and secondary endpoint to test the significance of the effects of the treatment at Week 52. The model includes treatment as fixed factor and the corresponding baseline value as a covariate.

A parametric Repeated Measures Analysis (RMA) Model will be applied as a secondary analysis to test the significance of the effects of the treatment at Week 4, Week 8, Week 16, Week 24, Week 32, Week 42 and Week 52 including baseline as covariate.

Presentation of results from a statistical analysis model will include the estimated mean treatment effects (Least Square Means (LSMeans)). For all endpoints analysed statistically, estimated mean treatment differences will be presented together with two-sided 95% confidence intervals and p-values,

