#### 5.2.2. Main analytical approach

Primary analysis
Endpoint/Variables

 
Change from baseline at Weeks 52 in Multiple Sclerosis Quality of Life (MSQOL)-54 Composite scores following treatment with HB-adMSCs or Placebo.
 

ANCOVA Model Specification

 
To compare the HB-adMSCs to Placebo on Change from baseline to Week 52, a standard Analysis of Covariance (ANCOVA) model will be fitted
 
Terms fitted in the mixed effect model will include: 
 
Primary endpoint efficacy measurements available at - Week 52 will be response variable in a linear mixed model using a variance-covariance residual matrix.
 
The model will include: 
 
Fixed factors: treatment
 
Fixed stratification factors: Multiple's sclerosis severity (Mild disability (EDSS < 4) ; Moderate disability (EDSS > 4 and < 6.5)), Age (< 55 ; > 55) and Gender (Female ; Male)
 
 
 
 
 

• Covariate: baseline

Model Checking and Diagnostics
For the ANCOVA Model assumptions will be checked, and appropriate adjustments may be applied based on the data.
Distribution assumptions underlying the model used for analysis will be examined by obtaining a normal probability plot of the residual and a plot of the residuals versus the fitted values (i.e., checking the normality assumption and constant variance assumption of the model respectively) to gain confidence that the model assumptions are reasonable.
Non-parametric analyses, Mann-Whitney U (or Wilcoxon Rank-Sum) Test will be conducted if the normality assumptions do not hold.
Results presentation
Presentation of results from a statistical analysis model will include the estimated mean treatment effects (Least Square Means (LSMeans)) and estimated mean treatment differences will be presented together with two-sided 95% confidence intervals standard error for mean difference and p-value.
Secondary analysis
Endpoint/Variables
Change from baseline in Multiple Sclerosis Quality of Life (MSQOL)-54 Composite scores following treatment with HB-adMSCs or Placebo at Week 4, Week 8, Week 16, Week 24, Week 32, Week 42 and Week 52.
Repeated Measures Model Specification

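### The MSQOL-54 composite counts a missing subscale as 0, the worst value, so the composite at that visit is too low by the subscale's weight times its true score

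*SAP*

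**What the plan says.** SAP 5.2.1 places every subscale on a common scale, "transforming the mean scores linearly from 0 to 100 possible scores, with higher scores indicating a better QOL". Under Derivation of MSQOL-54 Composite Scores, the two composites "are calculated as a weighted-sum using the subscale scores and the weights defined in table below". For a missing subscale the rule is that "it will not contribute to the Composite Score calculation (in effect, it is treated as a score of 0"). No minimum number of subscales, rescaling, imputation or sensitivity analysis is given for this case.

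SAP 5.2.2 defines the primary variable as "Change from baseline at Weeks 52 in Multiple Sclerosis Quality of Life (MSQOL)-54 Composite scores following treatment with HB-adMSCs or Placebo".

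Three other provisions bear on the point:

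- SAP 5.2.1 opens with a commitment: "Data from the MSQOL-54 will be scored according to the scoring algorithm suggested by the authors of the questionnaires". The algorithm is cited but not reproduced.
- SAP 5.1.2 says: "Unless otherwise stated, if baseline data is missing no derivation will be performed and baseline will be set to missing".
- SAP 5.1.1 says: "All continuous measurements will be summarised descriptively at each visit by treatment using observed data".

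**The concern.** On a scale where higher is better, 0 is the worst possible score. Leaving a term out of a weighted sum without rescaling the other weights therefore enters the worst value for a scale that was never observed. With Emotional Well-being (weight 0.29) missing, a patient with perfect scores elsewhere cannot exceed 71 on the mental composite. Health Distress is in both composites (0.11 and 0.14), so one missing scale distorts both.

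The rule always returns a number. The composite is not flagged as missing, and it enters the descriptive summaries and the primary ANCOVA as if it had been observed. With about 12 patients per arm, one affected patient can move an arm mean visibly.

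**Working it through.** **Inputs from the documents.** Weights: SAP table of composite weights. Scale 0–100, higher better: SAP 5.2.1. Change = post-baseline minus baseline: SAP 5.1.2. Up to 24 patients, 1:1: SAP sections 6 and 2.2. **Assumed:** the true subscale score, the missingness rates, SD of change 12, baseline–Week 52 correlation 0.6.

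**1. The plan's own statement.** Physical weights: 0.17 + 0.17 + 0.12 + 0.12 + 0.11 + 0.08 + 0.12 + 0.11 = 1.00. Mental weights: 0.14 + 0.18 + 0.29 + 0.24 + 0.15 = 1.00. For all 13 entries, omitting the term and entering 0 give the same composite, so the SAP describes its own rule correctly.

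**2. Error in one composite.** Shortfall = w × s (weight × true score). With every subscale truly 60, the true composite is 60.0.

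| Missing subscale | w | Composite under the SAP rule | Shortfall |
|---|---|---|---|
| Sexual Function | 0.08 | 55.2 | 4.8 |
| Physical Function | 0.17 | 49.8 | 10.2 |
| Health Distress (physical) | 0.11 | 53.4 | 6.6 |
| Health Distress (mental) | 0.14 | 51.6 | 8.4 |
| Emotional Well-being | 0.29 | 42.6 | 17.4 |

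Over true scores of 30 to 100 the shortfall is 2.4 to 8.0 for Sexual Function and 8.7 to 29.0 for Emotional Well-being. It is nil only if the true score is 0.

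**3. Error in the change score**, with s0 and s52 the true scores at baseline and Week 52:

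- Gap at Week 52 only: too low by w × s52.
- Gap at baseline only: too high by w × s0 if the composite rule overrides SAP 5.1.2. Otherwise baseline is missing and the patient leaves the ANCOVA.
- Gap at both visits: only that subscale's contribution, w × (s52 − s0), is lost.

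For a patient stable at 60, a Week 52 gap gives −4.8 to −17.4, a baseline gap +4.8 to +17.4, and a gap at both visits 0. One such one-visit gap in an arm of 12 moves the raw mean change by 4.8/12 = 0.40 to 17.4/12 = 1.45 points.

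**4. Chance that someone is affected at a visit.** 1 − (1 − rate)^24 gives 38%, 71% and 92% at assumed rates of 2%, 5% and 10%.

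**5. Trial level.** Planned ANCOVA simulated with 12 per arm: treatment, baseline and three binary strata, 18 residual df, lost score 60. Results are for weights 0.08 / 0.17 / 0.29.

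| Assumed pattern | Shift in treatment difference (points) | Operating characteristic |
|---|---|---|
| 10% in both arms, Week 52 | none when there is no effect | type I error 5.0%; power for a difference of 10 falls from 50% to about 49 / 47 / 43% |
| 10% placebo, 5% active, Week 52 | 0.2 / 0.5 / 0.9, favours active | type I error 5.0 / 5.1 / 5.3% |
| 20% placebo only, Week 52 | 1.0 / 2.0 / 3.5, favours active | type I error about 5.3 / 6.7 / 9.0% |
| 20% placebo only, both visits | 0.4 / 0.8 / 1.2, favours active | type I error about 5.0 / 5.1 / 5.7% |
| 20% placebo only, baseline, zero rule applied | 0.6 / 1.2 / 1.8, against active | – |

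Hand check of the third row: 0.20 × w × 60 = 0.96 / 2.04 / 3.48. In the fourth row the raw change of a stable patient is untouched, but the lowered baseline makes the ANCOVA expect a rise. With equal SDs at the two visits, about (1 − 0.6) × 0.20 × w × 60 = 0.38 / 0.82 / 1.39 remains. The simulated value at the heaviest weight is a little smaller because the affected patients alter the fitted slope.

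If SAP 5.1.2 prevails for a baseline gap, losing one patient (12 against 11) cuts power from 49.9% to 47.6%.

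**The case against.** The strongest reply is that nothing shows this will matter. The questionnaire is completed at clinic visits, and scale scores average their items, so one skipped item need not make a scale missing (the SAP does not say how many must be missing). The Protocol, under Unscheduled Visits, lets missed procedures be made up. Equal or mildly unequal missingness leaves the type I error at 5.0–5.3%. The 9% figure needs a fifth of placebo patients, no active patients, and the heaviest of 13 entries. A patient who habitually leaves a scale blank produces a gap at both visits, the mildest pattern. All of this stands, and it limits the severity.

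A second reply is that the rule is explicit, pre-specified and may come from the questionnaire's authors. That cannot be checked from the documents. It would not change the arithmetic, but it does decide the remedy.

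A reader might infer that no earlier assessment could ever fill a baseline gap. The documents do not settle this. In Protocol Table 4 the row "Multiple Sclerosis Quality of Life Inventory 54" starts at Visit 2, with no entry at screening. Yet the Protocol's Statistical Methods average MSQOL scores from screening and infusion 1, and the Investigational Plan counts screening among the visits for clinical assessment of disease activity. SAP 7.2.4 also admits unscheduled visits to the baseline derivation, although it does not slot them into post-baseline visit windows.

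**Conclusion.** The point holds: the rule is wrong as written, not merely under-specified. At any visit with a missing subscale the composite is too low by weight × true score. For a patient stable at an assumed 60, a gap at one visit gives a false change of 4.8 to 17.4 points in the primary variable.

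Two stronger readings are tempting and not supported. The first is that the primary change score is always too low: its error depends on the visit, and can be downward, upward, or only the loss of one subscale's change. The second is that the trial's result will be biased: the documents give no missingness rate, and the trial-level figures rest on assumed rates, SD, correlation and scores. This should be fixed because the per-patient error is certain wherever a gap occurs and the repair is cheap. It is not a demonstrated threat to the trial's conclusion.

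**What to change.** Before unblinding, check the rule against the scoring algorithm that SAP 5.2.1 commits to.

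If the algorithm does not prescribe the zero rule, replace the sentence with:

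> If a subscale is missing, the composite is the weighted sum of the available subscales divided by the sum of their weights. It is set to missing if less than a pre-specified share of the total weight is available. The same rule applies at baseline and at every post-baseline visit, and takes precedence over Section 5.1.2 for the composites.

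The share is for the sponsor to choose; the documents do not supply one.

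If the algorithm does prescribe the zero rule, keep it as the authors' score and add the re-weighted composite as a pre-specified sensitivity analysis.

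**Cost.** One sentence and a few lines of code, with no change to data collection. Some composites become missing. Re-weighting is not exact: it leaves an error of w × (m − s), where m is the weighted mean of the other subscales. At a 20-point gap that is 0.08 × 20 = 1.6 to 0.29 × 20 = 5.8 points. The error is smaller than under the zero rule whenever s is above m/2.

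In the stress case (20% in placebo only at Week 52, weight 0.29), mean gaps m − s of 0 / +20 / −20 leave a bias of 0.0 / −1.2 / +1.2 points and a type I error of 5.0 / 5.5 / 5.4%. The zero rule gives 3.5 points and about 9%. This check assumes a gap SD of 20 and a between-visit gap correlation of 0.6.

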#### 5.2.2. Main analytical approach

Primary analysis
Endpoint/Variables

 
Change from baseline at Weeks 52 in Multiple Sclerosis Quality of Life (MSQOL)-54 Composite scores following treatment with HB-adMSCs or Placebo.
 

ANCOVA Model Specification

 
To compare the HB-adMSCs to Placebo on Change from baseline to Week 52, a standard Analysis of Covariance (ANCOVA) model will be fitted
 
Terms fitted in the mixed effect model will include: 
 
Primary endpoint efficacy measurements available at - Week 52 will be response variable in a linear mixed model using a variance-covariance residual matrix.
 
The model will include: 
 
Fixed factors: treatment
 
Fixed stratification factors: Multiple's sclerosis severity (Mild disability (EDSS < 4) ; Moderate disability (EDSS > 4 and < 6.5)), Age (< 55 ; > 55) and Gender (Female ; Male)
 
 
 
 
 

• Covariate: baseline

Model Checking and Diagnostics
For the ANCOVA Model assumptions will be checked, and appropriate adjustments may be applied based on the data.
Distribution assumptions underlying the model used for analysis will be examined by obtaining a normal probability plot of the residual and a plot of the residuals versus the fitted values (i.e., checking the normality assumption and constant variance assumption of the model respectively) to gain confidence that the model assumptions are reasonable.
Non-parametric analyses, Mann-Whitney U (or Wilcoxon Rank-Sum) Test will be conducted if the normality assumptions do not hold.
Results presentation
Presentation of results from a statistical analysis model will include the estimated mean treatment effects (Least Square Means (LSMeans)) and estimated mean treatment differences will be presented together with two-sided 95% confidence intervals standard error for mean difference and p-value.
Secondary analysis
Endpoint/Variables
Change from baseline in Multiple Sclerosis Quality of Life (MSQOL)-54 Composite scores following treatment with HB-adMSCs or Placebo at Week 4, Week 8, Week 16, Week 24, Week 32, Week 42 and Week 52.
Repeated Measures Model Specification


• To compare the HB-adMSCs to Placebo on Change from baseline, a Repeated measures analysis (RMA) model will be fitted

• Terms fitted in the mixed effect model will include:

• All primary endpoint efficacy measurements available at post-baseline at scheduled measurements will be response variable in a linear mixed model using an unstructured residual covariance matrix.

• The model will include:

• Fixed factors: treatment and visit

• Fixed stratification factors: Multiple's sclerosis severity (Mild disability (EDSS < 4) ; Moderate disability (EDSS > 4 and < 6.5)), Age (< 55 ; > 55) and Gender (Female ; Male)

• Covariate: baseline

- Furthermore, the model will include:
  - Interaction terms between treatment and visit

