7. Visually confirm temperature tape is in biohazard bag and is within range (2° - 8° C), document compliance.
8. Visually confirm syringe is closed with cap.
9. Remove syringe from bag and begin mixing syringe, gently rocking back and as well as rolling between hands, bringing the study treatment to room temp, and suspending them into a homogenous solution. No particulates should be visible.
10. Inject the contents into a 250cc bag of normal saline for injection
11. Properly label the infusion bag with the subject ID, D.O.B, preparation date, time and expiration and cover it with an amber bag.

Once, the study treatment has been mixed by the unblinded pharmacist following the above procedures, the infusion nurse or designated study staff will administer the study treatment as follows:

1. Confirm that the subject number and DOB placed on the amber bag label belong to the subject receiving the infusion.
2. Administer the infusion solution over a period of 1h (infusion rate 4-5ml/min).
3. Do not store or reuse any unused portion of the infusion solution. Any unused product or waste material should be disposed in a biohazard container.
4. Complete the source documents of the visit to accurately collect the start and end times of the infusion and add comments if necessary.
5. The study's subject will be monitored for a total of 2 hours from drug exposure to discharge.
 - During the Investigational product administration (1 hour) vital signs will be measured at minute 0, 15, 30, 45, and 60.
 - Post infusion, vital signs will be measured at minute 90 and 120.
6. Follow study procedures as described in the schedule of assessments of the visit.

Investigational Product Assignment (Randomization and Blinding)

A total of 24 eligible subjects will be randomized to either placebo (approx. 12) or active drug (approx. 12) (HB-adMSCs) in a 1:1 balanced design. The randomization will be applicable only to eligible subjects. If a subject is not eligible during the screening process for study participation, this subject shall not be randomized to any group.

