## 4. ANALYSIS SETS

Population	Definition / Criteria	Analyses Evaluated
Safety analysis set	

• All randomised subjects who received at least one dose of HB-adMSCs infusion or placebo.

• If participants receive a treatment different to their randomized treatment, they will be analysed according to the treatment actually received.

	

• Safety

• Study Population

Efficacy analysis set	

• All randomized participants who received all 6 infusions of HB-adMSCs or placebo.

• Participants will be analysed according to their randomized treatment.

	

• Efficacy

Screened Population	

• This population consists of all subjects who signed an ICF to participate in the clinical trial.

• This population will be used for summarizing screening failures and reasons for screening failures.

	

• Study Population

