### **Primary analysis**

Primary analysis of Repeated Measures Analysis (RMA) Model will be performed for above secondary efficacy endpoints above as given in the Section [5.2.2](#).

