### **6. SAMPLE SIZE DETERMINATION**

Sample size consists of up to 24 subjects who have been diagnosed with Relapsing Remitting Multiple Sclerosis.

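### The repeated-measures model uses one baseline slope for all visits, so its Week 52 contrast may be imperfectly adjusted for baseline in the secondary MSQOL-54, Barthel and 9-Hole Peg analyses (low severity)

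*SAP*

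**What the plan says.** SAP 5.2.2 (Repeated Measures Model Specification) lists the terms: "Fixed factors: treatment and visit", the three stratification factors, baseline as a covariate, and "Interaction terms between treatment and visit". The residual covariance is unstructured. No baseline-by-visit term appears.

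The role of this model depends on the endpoint and on the section.

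- **MSQOL-54.** The lead analysis is an ANCOVA on Week 52 alone (SAP 5.1.1 and 5.2.2). Of the RMA, SAP 5.1.1 says: "A parametric Repeated Measures Analysis (RMA) Model will be applied as a secondary analysis".
- **Secondary efficacy endpoints.** SAP 5.3.1 says: "Primary analysis of Repeated Measures Analysis (RMA) Model will be performed for above secondary efficacy endpoints above", with ANCOVA second. SAP 5.1.1, however, names ANCOVA as the primary analysis for both the primary and the secondary endpoints. The two sections conflict.

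The schedule of assessments (Protocol Table 4) collects MSQOL-54, Barthel and 9-Hole Peg after baseline at Weeks 8, 24, 42 and 52. EDSS and PHQ-9 have one post-baseline assessment, at Week 52.

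**The concern.** The unstructured matrix lets variances and correlations differ freely between visits, yet the relation to baseline is held equal at Week 8 and Week 52. Those two choices sit poorly together.

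With equal SDs, the right slope on baseline at a visit is the correlation with baseline on the raw scale, or that correlation minus 1 on the change scale. If the correlation falls over the year, the right slope changes with it. A pooled slope is pulled towards the early visits, because their residual variance is smallest. Week 52 then gets a slope that is too large on the raw scale, which is the same as too little adjustment of the change score.

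With about 12 patients per arm, chance baseline differences are not small, and part of any such difference would pass into the Week 52 treatment estimate.

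**Working it through.** **Inputs from the documents.** The SAP says "Sample size consists of up to 24 subjects who have been diagnosed with Relapsing Remitting Multiple Sclerosis", and the Protocol allocates them "in a 1:1 balanced design", so about 12 per arm. On testing, "all hypotheses will be tested at a 2-sided significance level of 0.05 and 95% confidence interval". The efficacy set is "All randomized participants who received all 6 infusions of HB-adMSCs or placebo", so fewer than 24 may be analysed. No power, SD, effect size or baseline correlation is given, so there is no planned figure to reproduce.

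**Assumptions.** Unit SDs, normality, complete data at Weeks 8, 24, 42 and 52, and the correlation patterns named below.

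**Step 1: size of chance imbalance.** The SE of the baseline difference is sqrt(2/12) = 0.41 SD.

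**Step 2: the pooled slope, large sample.** Let beta be the vector of visit-specific slopes on the raw scale, S the residual covariance given baseline, and 1 a vector of ones.

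- Pooled slope: b = (1'S⁻¹beta)/(1'S⁻¹1).
- Error passed to Week 52 per unit of baseline imbalance: beta52 - b.
- Variance ratio, common slope over by-visit slopes: 1 + (beta52 - b)²/(1 - rho52²).

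Example with exponential decay to 0.5 at Week 52:

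- The slopes are 0.90, 0.73, 0.57 and 0.50, and the residual variances 0.19, 0.47, 0.67 and 0.75.
- The weights S⁻¹1/(1'S⁻¹1) are 0.87, 0.02, 0.02 and 0.10, so Week 8 dominates and b = 0.85.
- The error is 0.50 - 0.85 = -0.35 per unit.
- The variance ratio is 1 + 0.351²/0.75 = 1.16.

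Example with linear fade from 0.8 to 0.5: b = 0.723, the error is -0.22, and the ratio is 1 + 0.223²/0.75 = 1.07.

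**Step 3: simulation at N = 24.** Iterated GLS with unstructured covariance, 1,500 to 2,500 trials per pattern. The N = 24 column squares the simulated SE ratios (without strata / with three binary strata).

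| Correlation with baseline, Week 8 to 52 | beta52 - b | Variance ratio, large sample | Variance ratio, N = 24 |
|---|---|---|---|
| 0.7 throughout | 0 | 1.00 | 0.98 / 0.99 |
| 0.8 to 0.7, linear | -0.06 | 1.01 | 1.00 / 0.99 |
| 0.8 to 0.6, linear | -0.14 | 1.03 | 1.01 / 1.01 |
| 0.8 to 0.5, linear | -0.22 | 1.07 | 1.02 / 1.02 |
| 0.8 to 0.4, linear | -0.31 | 1.11 | 1.07 / 1.07 |
| 0.8 to 0.3, linear | -0.39 | 1.17 | 1.14 / 1.13 |
| 0.95 to 0.7, exponential | -0.23 | 1.11 | 1.07 / 1.08 |
| 0.90 to 0.5, exponential | -0.35 | 1.16 | 1.16 / 1.15 |
| 0.83 to 0.3, exponential | -0.42 | 1.19 | 1.14 / 1.14 |

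A separate simulation (3,000 trials per pattern) gave these SDs of the Week 52 estimate, common slope against by-visit slopes:

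- 0.89 to 0.56: 0.353 against 0.339, so (0.353/0.339)² = 1.08, with -0.28 units passed on per unit of imbalance.
- 0.88 to 0.42: 0.403 against 0.376, ratio 1.15, with -0.38 units.
- Constant 0.7: 0.293 against 0.297, ratio 0.97. Here by-visit slopes cost 2.7% in variance.

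Repeat runs of the two fading patterns gave 1.10 to 1.11 and 1.14 to 1.16.

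**Step 4: what that means in one trial.** A one-SE imbalance moves the Week 52 difference by 0.28 × 0.41 = 0.11 SD, or 0.38 × 0.41 = 0.16 SD. In variance terms, 8% and 15% are like losing 24 × (1 - 1/1.08) = 1.8 and 24 × (1 - 1/1.15) = 3.1 patients.

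**Step 5: power.** Take an assumed effect of 0.8 raw SD with rho52 = 0.5 (residual SD 0.866) and 12 per arm. Normal-approximation power is 61.9%. It becomes 61.0% if the SE rises 1.1% (0.8 to 0.5 fade, N = 24), 59.1% at +3.3% (same fade, large sample), and 55.3% at +8.1% (close to the steepest cases).

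**Step 6: bias.** The mean Week 52 estimate under no effect was essentially zero for every model and pattern.

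**The case against.** A reader might infer that the trial's main Week 52 result is poorly adjusted for baseline. It is not. The primary MSQOL-54 contrast is an ANCOVA on Week 52 data with its own slope. For EDSS and PHQ-9, with one post-baseline visit, the single slope already is the Week 52 slope. A reader might also infer bias, but the error averages to zero over randomisation. What remains is conditional on the imbalance in the one trial that is run.

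Nor can the RMA be called the lead model for Barthel and 9-Hole Peg without qualification: SAP 5.3.1 says so and SAP 5.1.1 says otherwise. If 5.1.1 governs, only supportive analyses are touched. SAP 5.3.1 also provides an ANCOVA for every secondary endpoint. With complete data and no strata, the by-visit RMA reproduces that ANCOVA exactly at Week 52. With strata included, the SAP's common-slope RMA was about as precise as the ANCOVA even under the two steep fades (SD 0.357 against 0.363, and 0.423 against 0.426), though the by-visit RMA did better (0.346 and 0.397).

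Finally, a single slope is a legitimate, more parsimonious choice with 24 or fewer patients, and the larger losses need a steep fade that the documents neither state nor rule out. All of this stands and limits the scope and the severity. It does not remove the mismatch between a free covariance and a fixed baseline slope, or the unequal trade: a small cost if correlation is stable, a larger gain if it fades.

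**Conclusion.** The point holds for the RMA only: the secondary MSQOL-54 analysis, and Barthel and 9-Hole Peg to the extent that SAP 5.3.1 governs. Bayesian Method 2, a supportive analysis, also has one baseline coefficient, but these calculations do not cover it.

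The SE ratios in the table run from about 1% lower to 8% higher. The 8% to 15% variance figures are for the two steep patterns and should not be read as expected values. Linear fades from 0.8 to between 0.7 and 0.5 gave almost no loss at this sample size, although a small residual dependence on baseline imbalance remained.

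All of this rests on assumed correlations, equal variances, normality and complete data; missing visits were not simulated. Severity is low: a cheap improvement, not a flaw in the primary analysis.

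**What to change.** 1. In SAP 5.2.2, add baseline by visit to the fixed effects of the RMA. SAP 5.3.1 inherits it by reference. Over the four collected visits this adds three parameters. If correlation with baseline is constant, the cost is about 1-3% in the Week 52 variance.
2. Reconcile SAP 5.1.1 with SAP 5.3.1 on whether ANCOVA or the RMA is the primary analysis of the secondary endpoints. If ANCOVA is chosen, the first change affects supportive analyses only, but is still worth making.

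Both are text changes, with one added model term and no new data. They should be made before unblinding, so that the choice of slope and lead model cannot depend on the results.
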